10. PK10-1 — $168 \text{ h} \pm 60 \text{ min}$ after the injection of BCD-131/Mircera[®]

11. PK11-1 — 216 h ± 120 min after the injection of BCD-131/Mircera®
12. PK12-1 — 288 h ± 120 min after the injection of BCD-131/Mircera®
13. PK13-1 — 336 h ± 120 min after the injection of BCD-131/Mircera®
14. PK14-1 — 504 h ± 120 min after the injection of BCD-131/Mircera®
15. PK15-1 — 672 h ± 120 min after the injection of BCD-131/Mircera®
16. PK16-1 — 840 h ± 120 min after the injection of BCD-131/Mircera®
17. PK17-1 — 1008 h ± 120 min after the injection of BCD-131/Mircera®
18. PK18-1 — 1176 h ± 120 min after the injection of BCD-131/Mircera®

In the group of volunteers receiving Aranesp®, blood sampling for the PK evaluation will be performed as follows:

1. PK1-1 — 5 min before the injection of Aranesp®
2. PK2-1 — 30 ± 5 min after the injection of Aranesp®
3. PK3-1 — 2 h ± 10 min after the injection of Aranesp®
4. PK3-1 — 8 h ± 15 min after the injection of Aranesp®
5. PK5-1 — 16 h ± 20 min after the injection of Aranesp®
6. PK6-1 — 24 h ± 20 min after the injection of Aranesp®
7. PK7-1 — 36 h ± 30 min after the injection of Aranesp®
8. PK8-1 — 48 h ± 30 min after the injection of Aranesp®
9. PK9-1 — 72 h ± 30 min after the injection of Aranesp®
10. PK10-1 — 96 h ± 60 min after the injection of Aranesp®
11. PK11-1 — 120 h ± 60 min after the injection of Aranesp®
12. PK12-1 — 168 h ± 60 min after the injection of Aranesp®
13. PK13-1 — 216 h ± 120 min after the injection of Aranesp®
14. PK14-1 — 288 h ± 120 min after the injection of Aranesp®
15. PK15-1 — 336 h ± 120 min after the injection of Aranesp®
16. PK16-1 — 504 h ± 120 min after the injection of Aranesp®
17. PK17-1 — 672 h ± 120 min after the injection of Aranesp®
18. PK18-1 — 840 h ± 120 min after the injection of Aranesp®

19. PK19-1 — 1008 h ± 120 min after the injection of Aranesp®
20. PK20-1 — 1176 h ± 120 min after the injection of Aranesp®

3.3 Time Points for Blood Sampling to Evaluate PK at Stage II of the Study

1. PK1-2 — 5 min before the injection of BCD-131
2. PK2-2 — 15 ± 3 min after the injection of BCD-131
3. PK3-2 — 30 ± 5 min after the injection of BCD-131
4. PK4-2 — 60 ± 5 min after the injection of BCD-131
5. PK5-2 — 2 h ± 10 min after the injection of BCD-131
6. PK6-2 — 4 h ± 15 min after the injection of BCD-131
7. PK7-2 — 8 h ± 15 min after the injection of BCD-131
8. PK8-2 — 24 h ± 20 min after the injection of BCD-131
9. PK9-2 — 48 h ± 30 min after the injection of BCD-131

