10. PK10-2 — 72 h ± 30 min after the injection of BCD-131
11. PK11-2 — 96 h ± 60 min after the injection of BCD-131
12. PK12-2 — 120 h ± 60 min after the injection of BCD-131
13. PK13-2 — 168 h ± 60 min after the injection of BCD-131
14. PK14-2 — 216 h ± 120 min after the injection of BCD-131
15. PK15-2 — 288 h ± 120 min after the injection of BCD-131
16. PK16-2 — 336 h ± 120 min after the injection of BCD-131
17. PK17-2 — 504 h ± 120 min after the injection of BCD-131
18. PK18-2 — 672 h ± 120 min after the injection of BCD-131
19. PK19-2 — 840 h ± 120 min after the injection of BCD-131
20. PK20-2 — 1008 h ± 120 min after the injection of BCD-131
21. PK21-2 — 1176 h ± 120 min after the injection of BCD-131

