7. STATISTICAL ANALYSIS OF POPULATION

Pharmacokinetics analysis

The pharmacokinetics (PK) analysis will include data of all volunteers who have received one dose of BCD-131 or reference drugs. If a subject has had more than two PK serum samples missed / lost / spoilt and skipped blood sampling time points more than twice, his/her data will not be included in the PK analysis.

Pharmacodynamics analysis

The pharmacodynamics (PD) analysis will include data of all volunteers who have received one dose of BCD-131 or reference drugs. If a subject has had more than two PK serum samples missed / lost / spoilt and skipped blood sampling time points more than twice, his/her data will not be included in the PD analysis.

Safety analysis

The safety analysis will include all patients who have received one dose of the test/reference drug.

Immunogenicity analysis

The immunogenicity analysis will include data of all volunteers who have received one dose of BCD-131 or reference drugs. If a subject has had serum samples taken on Day 1 and Day 50 missed / lost / spoilt, his/her data will not be included in the immunogenicity analysis.

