8.3. Accounting for missing, unavailable or doubtful data, outliers

All information specified in the e-CRFs should be supported by relevant data in source documents.

After entering all data into the electronic database, a database specialist checks it for inconsistencies, errors, and missing data points. The Clinical Study Database Manager or Medical Expert of JSC BIOCADC generates queries to correct error data or to request missing data; the queries are site-specific and subject-specific (i.e., individual queries are generated for each subject). The Clinical Study Monitor will send queries to the study site by fax or email. The queries should be resolved by the investigator within five business days from the date they have been submitted to the study site. Copies of responses to queries must be kept at the study site; original responses must be stored at JSC BIOCADC.

When responses to queries are received from investigators, the database specialist checks it for inconsistencies, errors, and missing data points. When all data at all study sites have been collected and entered, the database is closed. Afterwards, statistical processing can be started.

Missing, unused, and spurious data will not be substituted.

Spurious and unevaluable data are revealed during the outlier analysis by examination of Mahalanobis or Cook distance, visual analysis of scatter plots and box plots.

All actions taken to handle missing, unevaluable, spurious data and outliers before/during the statistical analysis will be described in the Clinical Study Report.

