8.4. The data conversion

Pharmacokinetic parameters

Based on determined concentrations in blood a number of the pharmacokinetic parameters will be calculated for the study drug:

1. **AUC₍₀₋₁₁₇₆₎**— area under the plasma concentration curve from administration to 1176 h:

- At stage I for BCD-131 and Mircera® products:

$$AUC_{(0-1176)} = \sum_{p=2}^{18} \frac{(C_p + C_{p-1}) * (t_p - t_{p-1})}{2},$$

where C_p – plasma concentration at the moment t_p (hours); $t_p \in \{0; 0.5; 2; 8; 24; 48; 72; 96; 120; 168; 216; 288; 336; 504; 672; 840; 1008; 1176\}; p=1, \dots, 18$

- At stage I for Aranesp® product:

$$AUC_{(0-1176)} = \sum_{p=2}^{20} \frac{(C_p + C_{p-1}) * (t_p - t_{p-1})}{2},$$

where C_p – plasma concentration at the moment t_p (hours); $t_p \in \{0; 0.5; 2; 8; 16; 24; 36; 48; 72; 96; 120; 168; 216; 288; 336; 504; 672; 840; 1008; 1176\}; p=1, \dots, 20$

- At stage II:

$$AUC_{(0-1176)} = \sum_{p=2}^{21} \frac{(C_p + C_{p-1}) * (t_p - t_{p-1})}{2},$$

where C_p – plasma concentration at the moment t_p (hours); $t_p \in \{0; 0.25; 0.5; 1; 2; 4; 8; 24; 48\}$

72; 96; 120; 168; 216; 288; 336; 504; 672; 840; 1008; 1176}; $p=1, \dots, 21$

2. C_{max} - maximum plasma concentration.
3. T_{max} - time until C_{max} is reached.
4. **Terminal rate constant (k_{el} , elimination constant)** will be calculated for the plasma concentration curve during the terminal log-linear phase by regression.
5. **AUC_(0-∞)** - area under the plasma concentration curve from administration to infinity:

$$AUC_{(0-\infty)} = AUC_{(0-1176)} + \frac{C_{1176}}{k_{el}},$$

where C_{1176} - plasma concentration at the moment 1176 h; k_{el} - elimination constant.

6. **Plasma concentration half-life ($T_{1/2}$)** will be calculated as:
 $T_{1/2} = \frac{\ln(2)}{k_{el}}$, where k_{el} - elimination constant.
7. **Total clearance (CL)** will be calculated as:

$$CL = \frac{D}{AUC_{(0-1176)}}, \quad \text{where } D \text{ - single dose of the drug product.}$$

Pharmacodynamic parameters

Based on reticulocyte counts and on hemoglobin values a number of key pharmacodynamic parameters will be calculated:

1. **AUEC₍₀₋₁₁₇₆₎** - (area under effect curve from the moment of injection to 1176 h [Day 50 of follow-up]) based on the change in the absolute reticulocyte count after a single-dose injection of the drug product::

$$AUEC_{(0-1176)} = \sum_{p=2}^{15} \frac{(C_p + C_{p-1}) * (t_p - t_{p-1})}{2},$$

where C_p the absolute reticulocyte count at the moment t_p (hours);

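### As worded, the PK-set exclusion rule never removes a volunteer who skips no time point, however many tubes are lost or spoilt, and the PD set inherits the same rule

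*SAP*

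**What the plan says.** SAP section 7 builds the PK set from everyone dosed: the "analysis will include data of all volunteers who have received one dose of BCD-131 or reference drugs". A volunteer is then removed if he had "more than two PK serum samples missed / lost / spoilt and skipped blood sampling time points more than twice". The protocol synopsis, under PK analysis, has the same sentence with the same *and*. Both documents repeat it for the PD set, where it still counts PK serum samples.

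The scheduled PK points end at "PK18-1 — 1176 h ± 120 min after the injection of BCD-131/Mircera" and "PK20-1 — 1176 h ± 120 min after the injection of Aranesp" in stage I (SAP 3.2), and at "PK21-2 — 1176 h ± 120 min after the injection of BCD-131" in stage II (SAP 3.3).

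On gaps in the data, SAP 8.3 says "Missing, unused, and spurious data will not be substituted" and then "All actions taken to handle missing, unevaluable, spurious data and outliers before/during the statistical analysis will be described in the Clinical Study Report". SAP 8.4 defines AUC(0-1176) as a linear trapezoid over the full fixed grid, and AUC(0-inf) from the "plasma concentration at the moment 1176 h". Neither document sets a minimum number of evaluable concentrations or says what to do with an absent grid point.

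**The concern.** An evaluability rule should ask whether enough of the curve is left to estimate the endpoint. This one asks for two things at once: samples missing, and visits skipped. Tubes haemolysed, lost in shipment or spoilt in the laboratory satisfy only the first, so a volunteer with perfect attendance passes the filter whatever the state of his profile. The cause of the gap decides the matter, although its effect on AUC is the same.

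AUC(0-1176) and AUC(0-inf) are the primary PK endpoints (SAP 4.1). SAP 8.4 derives AUC(0-inf) and CL from AUC(0-1176). A dose cohort without expansion has 3 volunteers (SAP 6), so one distorted curve carries a third of the cohort mean. Stage I is open-label and no threshold is fixed beforehand, so the handling of a damaged profile could be settled once results are visible.

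**Working it through.** **Grid counts (the plan's own figures).** The time lists in SAP 3.2 and 3.3 contain 18 points (BCD-131 and Mircera), 20 (Aranesp) and 21 (stage II). These match the upper limits of the three AUC sums in SAP 8.4. The PD grid there has 15 points.

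**The rule as logic.** Let s be the number of skipped time points and l the number of tubes lost or spoilt at attended points. Two readings of the sentence are possible:

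- Reading A, where missed samples include skipped points: exclude if (s + l > 2) and (s > 2).
- Reading B, where the two counts are separate: exclude if (l > 2) and (s > 2).

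| s | l | Reading A | Reading B | Single count s + l > 2 |
|---|---|---|---|---|
| 0 | 3 | kept | kept | excluded |
| 0 | 10 | kept | kept | excluded |
| 0 | 18 | kept | kept | excluded |
| 2 | 10 | kept | kept | excluded |
| 3 | 0 | excluded | kept | excluded |
| 3 | 3 | excluded | excluded | excluded |
| 15 | 2 | excluded | kept | excluded |

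Under reading A, s > 2 already implies s + l > 2, so the rule reduces to s > 2 and lost or spoilt tubes never matter. This was confirmed for all 190 combinations with s + l up to 18. Under reading B, even 15 skips with 2 spoilt tubes are kept. With s = 0, neither reading excludes anyone.

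**The PD set.** If no PK tube is missing, the first condition is false. No number of absent reticulocyte or haemoglobin values then triggers exclusion.

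**Size (illustration on assumptions).** The documents give no half-life or absorption rate. Assume C(t) proportional to ka/(ka - ke) × (exp(-ke·t) - exp(-ka·t)), with ke = ln 2 / half-life, half-life 50, 100 or 140 h, and ka 0.02 or 0.05 per h: six profiles. Apply the SAP trapezoid to the 18-point grid and join the neighbours of any absent point. For example, losing the 24-168 h tubes replaces everything between 8 and 216 h by (C8 + C216) × 208 / 2.

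Unfavourable consecutive blocks, change from the full-grid AUC(0-1176):

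- 48-96 h (3 tubes): -3.7% to -9.1%
- 24-120 h (5 tubes): -15.7% to -36.0%
- 24-168 h (6 tubes): -23.9% to -47.4%

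All patterns of interior loss (16 interior tubes, every set weighted equally, six profiles):

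- 2 lost (120 sets): range -12% to +10%
- 3 lost (560 sets): median absolute change 1.3%, 90th percentile 4.5%, under 5% in 91% of cases, range -21% to +23%
- 5 lost (4,368 sets): median absolute change 2.6%, under 5% in 73% of cases

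**Effect on a group mean.** With otherwise equal profiles, a 36% loss in one of 3 volunteers moves the mean by -36% / 3 = -12%. In a group of 6 it is -36% / 6 = -6%.

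**The case against.** Four points can be made for the plan.

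*The sentence sets membership of an analysis set only.* A reader might infer that a volunteer stays in the primary AUC however many tubes are lost. The documents do not say so. SAP 8.4 sums over every grid point, SAP 8.3 rules out substitution, and nothing tells the analyst to join neighbours across a gap. With nearly all tubes lost there would be no AUC to include. This objection stands: the supportable statement is that the rule does not exclude him.

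*The large errors are selected cases.* A reader might take -36% or -47% as typical. They come from consecutive blocks around the peak, mostly drawn on separate days, and scattered losses usually do far less. This also stands, and the figures are labelled accordingly.

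*The wording may simply be loose.* *And* may be a slip for *or*, and the immunogenicity sentence in SAP section 7 is similarly loose. That is plausible, but the same word appears for both sets in both documents and no text supports *or*. A programmer would implement it literally. For the same reason one should not claim to know which case the authors meant to catch.

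*The consequence for dose choice is limited.* The stage II dose is chosen for PD effects similar to the comparators, with PK and safety as further inputs, and the comparator and stage II groups have 6 volunteers. This stands as a limit: the documents do not support a claim that the selected dose would be wrong.

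**Conclusion.** The point holds as a defect in a stated rule. On either way of counting missed samples, lost or spoilt tubes cannot exclude a volunteer who skipped nothing, and no other provision fills the gap. That conclusion is purely logical and needs no PK assumption.

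The numerical effect does rest on assumptions: one-compartment profiles, parameter values absent from the documents, and linear bridging that the SAP does not specify. On those assumptions three scattered losses usually matter little, while a block around the peak can matter a great deal. The position of the lost tubes drives the error more than their number.

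The correction should be made before analysis, because it concerns the population for a primary endpoint and costs little. How much it changes will depend on how many tubes are lost and which.

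**What to change.** In SAP section 7 and the protocol's PK analysis paragraph, replace the double condition with a single count that keeps the sponsor's threshold: more than two scheduled PK concentrations unavailable for any reason (missed, skipped, lost or spoilt). Apply it to AUC and the parameters derived from it, and record the reason for each absent value before results are seen. For the PD set, in both documents, use the same single count on scheduled reticulocyte and haemoglobin values instead of PK serum samples.

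This costs one sentence per set in each document. The downside is that a volunteer with several laboratory losses can drop out of the AUC summary of a cohort of 3, a third of its data, in cases where the typical AUC change would have been about 1%. The sponsor should accept that knowingly.

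The count does not settle how AUC is computed across the one or two gaps still allowed, or what happens when the 1176 h value is absent. Each needs its own sentence in SAP 8.4.

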8. ANALYSIS PLAN AND STATISTICAL METHODS

8.1. The software

For statistical analysis and to construct the tables and diagrams would be used the software STATISTICA 10 and statistical programming language R.

8.2. Description of the Statistical Methods to be Employed

Quantitative Data

The following quantitative data will be analyzed in the study:

Pharmacokinetics:

- Plasma concentration of drug,
- Area under plasma concentration curve,
- Time (e.g., maximum plasma concentration time, half-life)

- Elimination parameters (e.g. clearance, terminal rate constant)

Pain Assessment:

- VAS score

Safety:

- CBC results,
- Blood chemistry results,
- Vital signs;
- ECG findings,
- Urea analysis results,
- Skin disorders size at the sites of venipuncture,
- Skin disorders lifetime at the sites of venipuncture.

Pharmacodynamics:

- absolute reticulocyte count.
- Hb level.
- Area under effect curve «absolute reticulocyte count — time».
- Area under effect curve «Hb level — time».
- Time (e.g. the time of the maximum increase of absolute reticulocyte count vs. baseline).

The statistical analysis will include two-tailed hypothesis testing; the chosen significance level is 0.05.

Quantitative variables will be tested for normality using the Shapiro-Wilk test.

Normally distributed quantitative variables will be tested using the two-sample Student's t-test, Welch's t-test, and ANOVA.

Non-normally distributed quantitative variables will be tested using the Mann-Whitney U-test, the Wilcoxon test, the Kruskal-Wallis test, and the Friedman test.

Normally distributed quantitative data will be described using the following descriptive statistics: mean, SD, CV, min, and max. Non-normally distributed quantitative data will be described using the following descriptive statistics: median, quartiles, CV, min, and max.

Categorical Data

The following categorical data will be analyzed in the study:

Safety:

- Skin disorders sort at the sites of venipuncture.
- Rate and severity grades of AEs/SAEs,
- Rate of Grade 3-4 AEs,
- Frequency of local reactions (total and by skin disorder type).
- Frequency of early study termination cases by AEs/SAEs.

Categorical data will be processed using frequency tables, contingency tables, the Fisher's exact test, the test of equal frequencies, Pearson's χ^2 test, and the Cochran-Mantel-Haenszel test. Percentages or proportions will be used to describe categorical data.

The Benjamini-Yekutieli correction for multiple testing will be used.

Statistical methods will be chosen according to the type of initial data and their distribution. Appropriate statistical tests will be established after the data collection has been completed because the type of data distribution, sample homogeneity, etc. are unknown before the study start. For appropriate data processing, the list of statistical methods used may expand during the analysis.

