8.5. Multivariate Comparison and Multiplicity

Refer to Section 8.2.

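### A normality pretest on groups of 3 to 6 picks the tests and summaries, and on its rank branch the dose-versus-comparator Mann-Whitney test cannot pass the Benjamini-Yekutieli correction in a family of five or more such tests

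*SAP*

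**What the plan says.** SAP 8.2 sets the framework: "The statistical analysis will include two-tailed hypothesis testing; the chosen significance level is 0.05". It then makes normality the gate: "Quantitative variables will be tested for normality using the Shapiro-Wilk test". If the variable passes, "Normally distributed quantitative variables will be tested using the two-sample Student's t-test, Welch's t-test, and ANOVA". If it fails, "Non-normally distributed quantitative variables will be tested using the Mann-Whitney U-test, the Wilcoxon test, the Kruskal-Wallis test, and the Friedman test". The summaries follow the same switch: mean and SD on one side, and on the other "Non-normally distributed quantitative data will be described using the following descriptive statistics: median, quartiles, CV, min, and max".

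On multiplicity, 8.2 says "The Benjamini-Yekutieli correction for multiple testing will be used", and section 8.5 adds only "Refer to Section 8.2". No family of tests is defined. Section 8.2 closes by leaving the choice open: "Appropriate statistical tests will be established after the data collection has been completed", and it allows the list of methods to grow during the analysis.

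The statistical methods paragraph of the protocol also chooses between parametric and rank tests by normality, and SAP section 10 declares no deviation from the protocol.

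SAP section 6 gives the sizes: 3 obligatory volunteers in each of seven dose cohorts, 3 more only if signs of dose-limiting toxicity appear, and 6 in each of the Mircera and Aranesp groups. SAP 3.1 bases the Stage II dose on a comparison of the BCD-131 doses with these two comparators.

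**The concern.** A normality test on three observations can hardly tell one distribution from another. Used as a gate, it lets chance decide which test and which summary each variable gets. If it is applied group by group, means may stand beside medians in the same dose table, which makes dose response harder to read.

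The rank branch has a separate problem. With so few volunteers, the exact Mann-Whitney p-value has a floor. If the floor lies above the corrected threshold, the result is known before any data are collected. The pairs at risk are the dose-versus-comparator pairs that inform the Stage II dose.

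Leaving the choice of test until the data of an open-label study are available removes the protection that a written plan should give.

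**Working it through.** **Plan's own figure.** The documents state no power, effect size or number of tests. The only size figure to reproduce is the maximum N: 7 x 6 + 12 = 54 at Stage I, and 54 + 12 = 66 overall. Both match. With no cohort expanded, N = 7 x 3 + 12 + 12 = 45.

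**Inputs from the documents.** Two-sided 0.05; 3 per dose cohort; 6 per comparator; Benjamini-Yekutieli (BY) correction.

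**Assumptions, not in the documents.** Pretest level 0.05; log-normal data with CVs of 30-80%; pretest run in each group; a BY family of 7 doses x 2 comparators = 14 tests for one endpoint.

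**Step 1: how informative the pretest is.** Shapiro-Wilk rejection rates from 10,000 simulated samples per case:

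| Data | n=3 | n=6 |
|---|---|---|
| Normal | about 5% | about 5% |
| Log-normal, CV 30% | about 5% | about 8% |
| Log-normal, CV 50% | 5-6% | about 12% |
| Log-normal, CV 80% | about 6% | 20-21% |

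At n=3 the rate hardly differs from that for normal data.

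**Step 2: how often a group switches.** There are nine Stage I groups (seven of 3, two of 6). If all are normal, P(at least one flagged) = 1 - 0.95^9 = 37%. At CV 30%, 1 - (0.950^7 x 0.924^2) = about 40%. At CV 80%, 1 - (0.94^7 x 0.80^2) = about 58%. Repeat simulations give roughly 40-60% over the CV range. Most of this switching would happen with normal data too.

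**Step 3: the Mann-Whitney floor.** The smallest exact two-sided p, under complete separation, is 2/C(n1+n2, n1):

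- 3 v 3: 2/20 = 0.10, above 0.05 even uncorrected.
- 3 v 6: 2/84 = 0.0238.
- 6 v 6: 2/924 = 0.00216.

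**Step 4: the BY threshold.** BY rejects the k smallest p-values if p(k) <= k x 0.05/(m x c(m)), where c(m) = 1 + 1/2 + ... + 1/m. The largest usable threshold, at k = m, is 0.05/c(m).

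| m | c(m) | 0.05/c(m) | Can 0.0238 pass? |
|---|---|---|---|
| 2 | 1.500 | 0.0333 | yes |
| 3 | 1.833 | 0.0273 | yes |
| 4 | 2.083 | 0.0240 | yes |
| 5 | 2.283 | 0.0219 | no |
| 7 | 2.593 | 0.0193 | no |
| 14 | 3.252 | 0.0154 | no |

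For m = 2 to 4, a family made up only of 3 v 6 tests rejects only if all m tests separate completely. From m = 5, no 3 v 6 test can reject, even if every dose separates completely from the comparator.

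**Step 5: exact or approximate p.** The SAP does not say which is used. For 3 v 6, the normal approximation gives a floor of 0.0201 without continuity correction and 0.0282 with it. The first can still pass at m = 5 and at m = 6 (0.05/2.45 = 0.0204) but not from m = 7; the second fails from m = 3. Both fail at m = 14. For 3 v 3, the uncorrected approximation gives z = 4.5/sqrt(5.25) = 1.964, p = 0.0495, so the statement that 3 v 3 can never reach 0.05 holds for the exact test.

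**Step 6: the rest of the rank branch.** With complete separation, Kruskal-Wallis gives p of about 0.0001 over all nine Stage I groups and 0.003 over the seven cohorts. Friedman with 3 volunteers over 15 times gives about 0.0001. For 6 v 6, one fully separated test is enough to reject for m up to 8, and two are enough at m = 14 (2 x 0.0011 = 0.0022, against 0.00216).

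**The case against.** **The whole rank branch is powerless.** A reader might infer this, and it is not so. Kruskal-Wallis, Friedman and the 6 v 6 comparisons (Stage II intravenous v subcutaneous, Mircera v Aranesp, or a cohort expanded to 6 v a comparator) can all reject, as can 3 v 6 in a family of four or fewer.

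**The family is not the plan's.** This stands. The SAP gives no m, so 14 is an assumption, and it needs all seven cohorts to enrol. The BY sentence also closes the text on categorical data. Its wording is general, however, and 8.5 sends all multiplicity to 8.2, so reading it as covering quantitative tests is reasonable. The missing family is a gap in itself.

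**The pretest may not be run per group.** This also stands. The SAP refers only to quantitative variables. On residuals pooled over 33 Stage I volunteers (7 x 3 + 2 x 6), simulation gives rejection in about 15-56% over the same CVs. The n=3 figures then do not apply, and each variable would have a single summary type. The Mann-Whitney floor is unchanged whenever that reading leads to rank tests.

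**Every dose will be reported as not different.** This goes beyond the documents. Per group, a given 3 v 6 pair enters the rank branch in about 13-25% of cases if either flagged group is enough. All 14 pairs enter essentially only if both comparators are flagged: about 0.08^2 = 0.6% to 0.20^2 = 4%. SAP 3.1 speaks of a comparison of pharmacokinetics, pharmacodynamics and safety; it nowhere says that non-significance means similarity. Nor would mixed tables be wholly incomparable, since CV, minimum and maximum are reported on both branches.

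**Conclusion.** The concern holds in limited form. The SAP lets a pretest select tests and summaries and leaves the final choice open. If run per group at 0.05, with CVs of 30-80%, the pretest rejects 5-6% at n=3 and 7-21% at n=6. At least one of nine groups switches in about 40-60% of trials, against 37% if all are normal.

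Where the rank branch is taken, the exact 3 v 6 Mann-Whitney test of a dose against a comparator cannot pass BY in a family of five or more such tests, and an exact 3 v 3 test cannot reject at all. The first result depends on a family size that the SAP does not define. It should not be read as a failure of all the rank tests, or as proof that the trial will declare every dose similar to the comparators.

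This is an exploratory Phase 1 study, but the comparison informs the Stage II dose, so the plan should be changed.

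**What to change.** Remove the normality gate and, before the Stage I data are analysed, fix one method per endpoint:

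- AUC, Cmax and AUEC: a log-scale model with ratios and 95% confidence intervals, with baseline as covariate for the pharmacodynamic endpoint.
- AC-Emax: an untransformed, baseline-adjusted difference with 95% confidence interval, because a log is undefined if a volunteer shows no increase.
- VAS pain score: also off the log scale, because zero is possible.

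Report the same summaries for every group. Base the dose comparison on estimates and intervals, and keep rank tests as sensitivity analyses. For any p-values that remain, either define the BY family or label them descriptive.

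An SAP edit alone is not enough, because the protocol's statistical methods paragraph also selects tests by normality. Change that paragraph to match, or declare the deviation in SAP section 10. The cost is a small wording change in both documents, with no effect on volunteers, sampling or timelines.
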